6.6.3 Safety data

From CTP Section 7.3: *For the safety data, including the primary endpoint, no missing data imputations are planned.*

For safety data that are not displayed by visit such as AE and possibly clinically significant laboratory abnormality, the following describes the approach to be used for the descriptive reporting:

- Original results (OR).

For safety data that are displayed by time point (or visit) of measurement, the following approach is to be used for the descriptive reporting:

- Observed cases (OC-IR) approach will be used, with no imputation for any missing data, which will include values after any rescue medication or treatment discontinuation (see [Section 6.3](#)).

The only exceptions where imputation might be necessary for safety evaluation are AE dates and start and stop dates for concomitant medications. Missing or incomplete AE dates are imputed according to BI standards ([4](#)).

Partial start and stop dates for concomitant medications, rescue and historical medication for PPP will be imputed to enable subsequent calculation (but not for display) by the following “worst case” approach:

- If the day of the end date is missing, then the end date is set to last day of the month (or to the patient's trial completion date, if it is earlier than the last day of the month).
- If the day and month of the end date are missing then the end date is set to 31st of December of the year (or to the patient's trial completion date, if it is earlier than the 31st of December of the year).
- If the day of the start date is missing the start date is set to first day of the month (except for rescue therapy, where the first dosing day will be used if first dosing happened in the same month).
- If the day and month of the start date are missing then the start date is set to 1st January of the year (except for rescue therapy, where the first dosing day/month of study medication will be used if first dosing happened in the same year).
- All other cases need to be assessed by the trial team on an individual basis, using the above points as guidance.

If a concomitant medication was ticked to be ongoing, it is expected that the end date is missing and will not be imputed for display purposes.

6.6.6 Time since first diagnosis/tonsillectomy

Time since first diagnosis is derived as specified in [Section 5.4.2](#). The handling of missingness will follow the rule implemented in the parent trial described as below.

For incomplete information on the date of first diagnosis, time since first diagnosis will be calculated as follows:

- If the year of first diagnosis is unknown, time since first diagnosis will be set to missing.
- If day and month of the first diagnosis are unknown, time since first diagnosis will be calculated as if diagnosed on the 30th June of that year.
- If only the day of the first diagnosis is unknown, time since first diagnosis will be calculated as if diagnosed on the 15th of that month.

Time since tonsillectomy will be imputed in the same way.

6.7 BASELINE, TIME WINDOWS AND CALCULATED VISITS

Measurements reported with date and time and taken prior to start of administration of trial treatment will be considered pre-treatment values. Measurements reported with a date only (and no time) and taken on the day of first administration of trial treatment will also be considered pre-treatment values. These pre-treatment values will be assigned to visits according to the nominal visit number as recorded on the eCRF or as provided by the laboratory.

Baseline, unless otherwise specified, is defined as the last measurement collected prior to the start of administration of the trial treatment.

Baseline for “change from baseline” or “compared to baseline” types of efficacy endpoints , unless otherwise specified, is defined as the last measurement collected prior to the start of administration of the trial treatment in the parent trial. Baseline for time to event endpoints, is defined as the last measurement collected prior to the start of administration of the trial treatment in the current extension trial.

Measurements taken after start of administration of trial treatment will be considered either on- or off-treatment values based on the definition in [Section 6.1](#), and will be assigned to visits for statistical analysis, if applicable, as defined below.

Analysis of AE data, potentially clinically significant abnormal laboratory values, concomitant medication, or non-drug therapies, as well as use of rescue therapy will not be based on visits. Frequency tables for these data will be using on-treatment data and categorized based on their occurring/starting dates. Therefore, no assignment to time windows will be necessary for such data.

The derivation of the last value, minimum value and maximum value of laboratory and vital signs data will consider all on-treatment values (whether or not selected in any time window; see [Table 6.1: 1](#) for definition of the on-treatment period) within the period of interest; these will be derived for analysis of laboratory and vital signs data. For identification of potentially clinically significant abnormal laboratory values, all values (whether or not selected in any time window) within the on-treatment period will be considered.

All other safety, efficacy [REDACTED] measurements will be assigned to visits based on extended time windows around the planned visit dates, defined relative to the day of first trial treatment (which is scheduled for Visit V2).

The extended time windows for vital signs are defined in [Table 6.7: 1](#) and the extended time windows for efficacy, safety lab, [REDACTED] measurements are defined in [Table 6.7: 2](#).

Table 6.7: 1 Time windows for assignment of vital signs to visits for statistical analysis

Visit number /name	Visit label	Planned day	Time window (Days)					
			Window (per CTP)	Start (per CTP)	End (per CTP)	Start (extended)	End (extended)	
V1*	Screening	-28 to -1	n/a					
V2*	Day 1	Day 1	+/-0	1 ^A	1 ^A	≤1 ^A	1 ^A	
Planned On-Treatment Data								
V3	Week 4	Day 29	+/-7	22	36	2	43	
V4	Week 8	Day 57	+/-7	50	64	44	71	
V5	Week 12	Day 85	+/-7	78	92	72	99	
V6	Week 16	Day 113	+/-7	106	120	100	127	
...	Planned date-7	Planned date+7	End of extended window of last visit+1	Midpoint of planned days between current visit and next visit LD ^B +112	
V67/ EOT	Week 260/ EoT	Day 1821	+/-7	1814	1828	End of extended window of last visit+1		
Planned Off-Treatment Data								
EOS	Week 276/ EoS	Day 1933	+7	1933	1940	LD ^B +113	Day of last f-up value	

Days are counted relative to the day of first s.c. treatment in maintenance period, which is defined as Day 1 for maintenance.

* For the patients who enter OLE trial, V1 is strongly recommended to be performed during the EOT of the preceding parent trial, and the maximum days allowed between EOT of parent trial and V1 is 28 days (may be extended on a case by case basis); V2 is considered as/identical to the EOS of parent trial.

^A Note that measurements made at Day 1 and assigned to the on-treatment period (because mistakenly made after start of infusion of trial treatment) via assessment on date and time (i.e. safety laboratory) will not be assigned to Day 1. Such data will be listed only.

^B LD=Day of last maintenance treatment received.

Table 6.7: 2 Time windows for assignment of efficacy, safety lab, [REDACTED] measurements to visits for statistical analysis

Visit number /name	Visit label	Planned day	Time window (Days)				
			Window (per CTP)	Start (per CTP)	End (per CTP)	Start (extended)	End (extended)
V1*	Screening	-28 to -1	n/a				
V2*	Day 1	Day 1	+/-0	1 ^A	1 ^A	≤1 ^A	1 ^A
Planned On-Treatment Data							
M1	Week 16	Day 113	+/-7	106	120	2	169
M2	Week 32	Day 225	+/-7	218	232	170	281
M3	Week 48	Day 337	+/-7	330	344	282	393
M4	Week 64	Day 449	+/-7	442	456	394	505
...	Planned date-7	Planned date+7	End of extended window of last visit+1	Midpoint of planned days between current visit and next visit
M16	Week 256	Day 1793	+/-7	1786	1800	1738	1807
M17/ EOT	Week 260/ EoT	Day 1821	+/-7	1814	1828	End of extended window of last visit+1	LD ^B +112
Planned Off-Treatment Data							
EOS	Week 276/ EoS	Day 1933	+7	1933	1940	LD ^B +113	Day of last f-up value

Days are counted relative to the day of first s.c. treatment in maintenance period, which is defined as Day 1 for maintenance.

* For the patients who enter OLE trial, V1 is strongly recommended to be performed during the EOT of the preceding parent trial, and the maximum days allowed between EOT of parent trial and V1 is 28 days (may be extended on a case by case basis); V2 is considered as/identical to the EOS of parent trial.

^A Note that measurements made at Day 1 and assigned to the on-treatment period (because mistakenly made after start of infusion of trial treatment) via assessment on date and time (i.e. safety laboratory) will not be assigned to Day 1. Such data will be listed only.

^B LD=Day of last maintenance treatment received.

Repeated and unscheduled efficacy, safety [REDACTED] measurements will be handled similarly to scheduled measurements and will also be assigned to a time window depending upon the date of measurement.

Only one observation per time window will be selected for statistical analysis at a particular visit – the value which is closest to the protocol planned visit day will be selected. If there are two observations which have the same difference in days to the planned day, the later value will be selected. If there are two observations on the same day, the worst value will be selected.

Assignment of efficacy observations to visits based on time windows will be based on the non-imputed (observed) data after the implement of estimand concepts. For example, for the

OC method, values after rescue therapy intake or 6 weeks following last treatment in case of discontinuation should be censored first before assignment of efficacy endpoints.

For visits without an assigned value based on time windows, a value will thereafter be imputed (if needed) as defined in [Section 6.6](#). Imputation of efficacy endpoints, when applicable, will be performed based on all available observations meeting the imputation rules, irrespective of whether the observation was selected in any time window.

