## Trial Design

[figure not shown]

Figure 3.1: 1 One single arm: Spesolimab (BI 655130) 600mg s.c. q4w over 260 weeks

For patients who terminate study drug prematurely in this extension study the subsequent visit will be replaced by an early EoT visit followed by an EoS visit 16 weeks after the last study drug administration (see Figure 3.1: 1).

Interim analyses of [REDACTED] and clinical data may be performed throughout the conduct phase of this 5-year study to support future trial applications, investigator brochures, regulatory documents and scientific publications. The final analysis of the entire trial data will be performed once all patients have completed the last scheduled trial visit. Individual patient participation is concluded when the patient has completed the last scheduled visit. The end of whole study is defined as “last patient out”; i.e. last scheduled visit completed by the last patient in the study.

An independent Data Monitoring Committee will evaluate safety and efficacy data on a continuous basis.

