### 5.2.2 Vital signs

Vital signs will be evaluated at the time points specified in the [Flow Chart](#), prior to blood sampling. At dosing visits, vital signs evaluations will be performed pre-dose and additional evaluation will be taken at approx. 10 minutes post-dose.

This includes systolic and diastolic blood pressure and pulse rate (electronically or by palpation count for 1 minute) in a seated position after 5 minutes of rest, and additionally temperature and respiratory rate. The results must be included in the source documents available at the site.

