### **6.2.3 Follow-up period and trial completion**

For all patients, termination of trial medication and trial completion must be recorded on the corresponding eCRF.

For patients completing the safety FU period, the EoS visit is scheduled at 16 weeks after the last dose of study drug. For more details please follow [Flow Chart](#).

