6. GENERAL ANALYSIS DEFINITIONS

6.1 TREATMENT(S)

The following maintenance treatment is planned in this study:

Spesolimab 600 mg q4w s.c. for up to 5 years for patients who have completed and clinically responded to the treatment with study drug (Spesolimab) in previous trials.

The following study phases are defined:

Table 6.1: 1 Flow chart of analysis phases of the study

Study analysis phase	Description	Start (included)	End (included)
Screening phase	Screening	Earliest of i) Date of informed consent, ii) First screening procedure	Date/time of start of injection for maintenance study drug minus 1 second
Maintenance treatment phase & Residual effect period	Maintenance on-treatment period	Date/time of start of injection of first maintenance study drug (Day 1 for maintenance)	Earliest of: i) Date of injection of last maintenance study drug + 112 days at 23:59, ii) cut-off for interim analysis if applicable.
Follow-up ¹ phase	Off-treatment period	Date of injection of last maintenance study drug + 113 days at 12:00 a.m.	Latest of: i) Date of EOS visit (Week 276 visit); ii) Last contact date on End of Study page at 11:59 p.m.

Dates are defined individually per patient. If more than one date is associated with a specific visit, measurements associated with a specific date are assigned to a study analysis phase according to the rules specified in the table. An analysis phase will not extend beyond the start date of the following phase.

¹ The follow-up phase only exists if the date of EOS visit or the last contact date is after the date of injection/infusion of last study drug + 112 days.

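### In SAP 6.7 the EoS window excludes its own target day and the same-day rule pools pre-dose and post-dose vital signs; SAP 7.8 and 7.8.2 also disagree on follow-up laboratory data

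*SAP*

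**What the plan says.** **Visit assignment.** Apart from data not analysed by visit, such as adverse events, SAP 6.7 says that "measurements will be assigned to visits based on extended time windows around the planned visit dates", counted from the first dose in the extension. One observation per window is kept: the one nearest the planned day, the later one if two are equally distant, and the worst one if two fall on the same day.

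**EoS.** Protocol 6.2.3 says "the EoS visit is scheduled at 16 weeks after the last dose of study drug", and the Flow Chart allows up to 7 days later and none earlier. For patients who stop early, Protocol 3.1 says "the subsequent visit will be replaced by an early EoT visit followed by an EoS visit 16 weeks after the last study drug administration". In SAP Tables 6.7:1 and 6.7:2 the EoS row stands under "Planned Off-Treatment Data". It has planned Day 1933, a protocol window of Days 1933 to 1940, and an extended window that starts at LD+113, where LD is the day of the last dose. The EoT row runs to LD+112. SAP Table 6.1:1 ends the on-treatment period at "Date of injection of last maintenance study drug + 112 days at 23:59", and its footnote adds: "The follow-up phase only exists if the date of EOS visit or the last contact date is after the date of injection/infusion" of the last dose plus 112 days. For safety data shown by visit, SAP 6.6.3 uses the OC-IR approach, "which will include values after any rescue medication or treatment discontinuation".

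**Vital signs.** Protocol 5.2.2: "At dosing visits, vital signs evaluations will be performed pre-dose and additional evaluation will be taken at approx. 10 minutes post-dose". Baseline in SAP 6.7 is the last measurement before treatment starts. SAP 7.8.3 plans summaries over time and change from baseline, and adds no selection rule.

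**Follow-up laboratory data.** SAP 7.8 restricts off-treatment data to listings. SAP 7.8.2 plans by-visit laboratory statistics that include follow-up.

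**The concern.** An extended window should contain the protocol window it extends. The EoS window opens one day after its own planned day, so the row in which an EoS visit is tabulated depends on whether it took place on day 112 or day 113 after the last dose. A reader of the Week 64 row could be looking at an end-of-study value from a patient who stopped treatment 16 weeks earlier.

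For vital signs, a rule suited to accidental repeats is applied to a pair that the protocol plans at every dosing visit. The by-visit mean change would then mix pre-dose and post-dose readings, and would select the more extreme of the two.

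The two laboratory statements leave open whether follow-up values are summarised at all. Long-term safety is the main purpose of this trial and repeated interim outputs are planned, so two programmers should not be able to produce different tables from the same SAP.

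**Working it through.** **1. EoS row**

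Inputs: planned day = 7 × week + 1 (Flow Chart); extended end = midpoint of adjacent planned days, and extended start = previous end + 1 (SAP Tables 6.7:1 and 6.7:2); EoS due at LD+112 to LD+119.

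Reproducing the plan's figures:
- EoT: 7 × 260 + 1 = 1821. EoS: 7 × 276 + 1 = 1933 = 1821 + 112.
- Laboratory windows: Week 48 ends at (337 + 449)/2 = 393, so it is 282–393. Week 64 ends at (449 + 561)/2 = 505, so it is 394–505. Week 256 ends at (1793 + 1821)/2 = 1807, so Week 260 starts on Day 1808. These agree with the printed limits and the stated rule.
- Vital signs by the same rule: Week 52 is 352–379 and Week 64 is 436–463.

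Applying the tables to a target-day visit and to one a day later:

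| Last dose | EoS day | Laboratory row | Vital-sign row |
|---|---|---|---|
| 1821 (Week 260) | 1933 = LD+112 | Week 260, 112 days from plan | Week 260, 112 days from plan |
| 1821 | 1934 = LD+113 | EoS | EoS |
| 337 (Week 48) | 449 = LD+112 | Week 64, 0 days from plan | Week 64, 0 days from plan |
| 337 | 450 = LD+113 | EoS | EoS |
| 365 (Week 52) | 477 = LD+112 | Week 64, 28 days from plan | Week 68, 0 days from plan |

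- Completer: an EoT value on Day 1821 is at distance 0 and is selected, so the EoS value leaves the by-visit table. This does not depend on exact dosing. With the last dose anywhere in Days 1814–1828, LD+112 is Day 1926–1940, always inside Week 260.
- Early stopper, last dose Day 337: if the early EoT is held at the next planned visit (Day 365, an assumption), it falls in Week 48 for laboratory data and Week 52 for vital signs. The EoS reading is then the only planned value in the Week 64 window.
- Seven of the eight permitted days map to EoS. The one that does not is the target day.

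**2. Vital signs**

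Dosing every 4 weeks from Week 4 to Week 260 gives 260/4 = 65 post-baseline visits with a planned same-day pair. If higher is taken as worse, the selected value is max(pre, post), and

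max(pre, post) − pre = max(post − pre, 0) ≥ 0

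for every patient. Compared with a pre-dose-only summary, mean change can move only towards the worse side, and it does so whenever some post-dose readings exceed their pre-dose partner. If lower is taken as worse, the sign reverses. The size depends on the mean post-minus-pre difference, the SD and the within-visit correlation. The documents give none of these, so no figure is offered.

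**3. Follow-up laboratory data**

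SAP 7.8 and 7.8.2 cannot both be applied to laboratory values after LD+112. The two tables in SAP 6.7 also define an EoS window for statistical analysis, which a listing-only rule would not need. The first point compounds this. Under SAP 7.8, an early stopper's vital signs on day 112 are summarised as a treatment visit, and those on day 113 are only listed.

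**The case against.** **EoS.** The fair defence is that LD+112 is on-treatment by design and that OC-IR openly includes values after discontinuation. Both are correct. A reader might infer that the plan misclassifies the end of treatment. It does not: the SAP Table 6.1:1 limit and its footnote match the 16-week residual effect period. What remains is only the row in which the visit is shown. It is also true that a completer's lost EoS value costs little, since under SAP 7.8 it would be listed anyway, except for laboratory data if SAP 7.8.2 governs.

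**Vital signs.** Stronger readings are tempting, and the documents do not support them.
- A reader might infer that no rule covers same-day readings. One does: the worst value. The later-value rule overlaps it literally, since same-day readings are equally distant from the planned day, but it is more naturally read as covering readings on either side of that day.
- A reader might infer that planned Day 1 post-dose readings are barred from summaries by footnote A of Table 6.7:1. That note concerns values taken after dosing by mistake, which planned post-dose readings are not.
- A bias in mmHg could be calculated, but only from invented inputs.

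Three things do count for the plan. SAP 6.6.3 allows display by time point or by visit, SAP 7.8 recognises post-dose vital signs as a scheduled item, and the sponsor's internal standards may define a direction for the worst value. None of these appears in the documents as a rule that separates the two sets.

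**Laboratory data.** The specific section probably governs the general sentence, but the SAP does not say so.

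**Conclusion.** The point holds as a minor one. The EoS window excludes its own target day, one of eight permitted days. The share of EoS visits held on that day cannot be known from the documents. The worst-value rule, applied to 65 planned pairs per completer, pools two time points, lacks a direction for two-sided parameters such as blood pressure, pulse and temperature, and compares a worst-of-two value with a single pre-dose baseline. The direction of the shift follows from the rule once worst is defined; its size cannot be derived. SAP 7.8 and 7.8.2 conflict.

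The consequences stay within descriptive by-visit safety tables. Treatment-emergent adverse events are not assigned to visit windows. In early stoppers the primary (OC) efficacy summaries are protected, because values more than 6 weeks (42 days) after the last dose are removed before windows are applied, and 112 exceeds 42. Completers with an EoT assessment keep that value. Minimum and maximum values use all on-treatment readings. Every individual value is listed, and clinically relevant vital-sign findings are analysed as adverse events.

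**What to change.** 1. In SAP Tables 6.7:1 and 6.7:2, assign the EoS visit to the EoS row by nominal visit, for completers and early stoppers alike. SAP 6.7 already uses nominal visits for pre-treatment values. Keep the LD+112 on-treatment definition for adverse events and for last, minimum and maximum values. Relabel or footnote the off-treatment heading above the EoS row, so that a target-day visit can be on-treatment by date and still be shown as EoS.
2. In SAP 6.7 and 7.8.3, select vital signs within planned time point. Summarise pre-dose change from the pre-dose baseline by visit and show post-dose values separately. Limit the worst-value rule to true repeats and state a direction for each parameter.
3. State in SAP 7.8 whether the laboratory summaries in SAP 7.8.2 are an exception to listing only.

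The cost is a few sentences, light programming and one extra vital-signs display. No new data are needed, and the visit schedule does not change.

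### Planned pre-dose and post-dose vital signs compete for one value per visit under SAP 6.7, with no order between the two tie rules and no direction for the worst value (minor; by-visit tables only)

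*SAP*

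**What the plan says.** **Collection.** Protocol 5.2.2, Protocol 6.2.2 and flow chart footnote 7 all require vital signs before dosing and again about 10 minutes afterwards at each dosing visit. Protocol 6.2 lists the post-dose reading as a separate last step of the visit. Drug is given at every visit from V2 to EoT (V67).

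**Assignment to visits.** SAP 6.7 states: "The extended time windows for vital signs are defined in" Table 6.7: 1. That table has one row per visit and does not separate pre-dose from post-dose. The selection rule is: "Only one observation per time window will be selected for statistical analysis at a particular visit". The value nearest the planned day is taken. If two values are equally near, the later one is taken. Then: "If there are two observations on the same day, the worst value will be selected".

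**Baseline.** "Baseline, unless otherwise specified, is defined as the last measurement collected prior to the start of administration of the trial treatment". For vital signs this is a single reading before the first extension dose.

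**Day 1.** Footnote A to Table 6.7: 1 concerns "measurements made at Day 1 and assigned to the on-treatment period (because mistakenly made after start of infusion of trial treatment"). It refers to safety laboratory data and says these values "will not be assigned to Day 1. Such data will be listed only". The V3 window opens on Day 2.

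**Output.** SAP 7.8.3 plans descriptive statistics of vital signs over time and of differences from baseline, and refers to 6.7. SAP 7.8 mentions scheduled post-dose vital signs only to classify same-day values as before or after treatment when no time is recorded.

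**The concern.** A same-day tie rule normally deals with an accidental repeat. Here two same-day readings are the plan at every dosing visit, so the rule decides what enters the by-visit tables for nearly every patient and visit.

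This raises three difficulties. First, the rule cannot be programmed uniquely. Two same-day readings are equally far from the planned day, so they meet both the later-value and the worst-value sentences. Worst also has no direction for blood pressure, pulse, temperature or respiratory rate, each of which can be abnormal high or low. Second, if the worst value is used, a reading chosen from two is compared with a baseline that was not chosen, and mean change can move with no drug effect. The trial has a single arm, so no comparator would show this. Third, the post-dose reading, which the protocol collects on purpose, could not be recognised as such in the by-visit tables.

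Interim outputs may feed investigator brochure updates, submissions and publications (Protocol 7.2.7), so the same tables could be issued several times.

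**Working it through.** The documents give no figure to reproduce for this point and no SD for any vital sign. All SDs below are assumptions.

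**1. How many visits.** Dosing visits V2 to V67: 67 - 2 + 1 = 66. Post-baseline dosing visits V3 to V67: 67 - 3 + 1 = 65.

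**2. Windows.** The midpoint rule reproduces Table 6.7: 1. For Week 4 (Day 29) and Week 8 (Day 57), (29 + 57)/2 = 43, so V3 runs from Day 2 to 43 and V4 starts on Day 44. The planned pair at a visit falls on one day and so in one window. A Day 1 post-dose reading is not in the V3 window.

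**3. Which rule applies.** Both readings have the same distance in days to the planned day, so the later-value rule selects the post-dose reading. Both are on the same day, so the worst-value rule selects the worse one. The worst-value rule is the more specific and the likelier reading, but the SAP does not say that it takes precedence.

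**4. Size if the later value is used.** There is no selection effect. Post-dose values are compared with a pre-dose baseline, so mean change includes any true 10-minute change, and is 0 if there is none.

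**5. Size if the worst value is used and is one-sided.** Take two exchangeable normal readings around the visit mean, with within-visit SD s, and no drug effect. The expected maximum exceeds the mean by

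s / sqrt(pi) = 0.564 x s

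- s = 4 mmHg: 0.564 x 4 = 2.26 mmHg
- s = 8 mmHg: 0.564 x 8 = 4.51 mmHg

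The shift is negative if worst means lowest. Simulation (2,000,000 draws, patient means N(0, SD 10) around a reference, single-reading baseline) gives the same figures to within 0.01 for visit-to-visit SDs v of 0, 5 and 8 mmHg. The shift depends on s alone.

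With an assumed true post-dose rise of 2 units (independent readings, v = 0), the one-sided shift is +3.4 (s = 4) to +5.6 (s = 8) if worst means highest. If worst means lowest, it is -1.4 to -3.6.

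**6. Size if the worst value is used and is two-sided** (the reading further from the reference, patient means centred on it). Mean change stays within about 0.01 of 0. The SD of change rises:

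| s | v | SD, single pre-dose | SD, worst of two | Rise |
|---|---|---|---|---|
| 4 | 0 | 5.65 | 5.89 | 4.3% |
| 4 | 5 | 9.05 | 9.60 | 6.1% |
| 4 | 8 | 12.65 | 13.40 | 6.0% |
| 8 | 0 | 11.30 | 12.17 | 7.6% |
| 8 | 5 | 13.35 | 14.52 | 8.8% |
| 8 | 8 | 16.01 | 17.48 | 9.2% |

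**7. With pre-dose readings on both sides.** Under no true change, the expected mean change is 0 for every s and v.

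**The case against.** **The rule may be meant for repeats only.** It follows directly on the sentence about repeated and unscheduled measurements. SAP 6.6.3 speaks of safety data "displayed by time point (or visit) of measurement", and SAP 7.8 recognises post-dose vital signs as a scheduled assessment. Separate time points may well be intended. But SAP 6.7 says that repeats are handled like scheduled measurements, so the rule covers scheduled ones too, and none of these places exempts the planned pair.

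**Sponsor standards may settle it.** SAP 7.8 says that safety analyses follow them, and parts of the SAP are redacted. This stands as a limit on the point. The visible text cites guidance on repeat values at one visit only for laboratory data (7.8.2), and none in 7.8.3.

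**Footnote A.** A reader might infer that the planned Day 1 post-dose reading is excluded and only listed. The footnote does not clearly support that. It speaks of values taken by mistake after an infusion and refers to safety laboratory data, whereas these readings are planned and follow an injection. What can be said is that Table 6.7: 1 does not show where they go.

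**Pooling.** A reader might also infer that the two readings are pooled or averaged. They are not: the rule selects one.

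**Extremes are still captured.** This stands. "The derivation of the last value, minimum value and maximum value of laboratory and vital signs data will consider all on-treatment values", all individual values are listed, and findings judged clinically relevant are reported as AEs. An abnormal post-dose reading would not be lost.

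**Conclusion.** The point holds as a minor one. On the visible text, the planned pre-dose and post-dose readings compete for one slot at up to 65 post-baseline visits, under two tie rules without an order and an undirected worst value. Under either rule, by-visit change from baseline is not a like-for-like pre-dose comparison.

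With no drug effect and exchangeable readings, the mean shift under the worst-value rule ranges from 0 to 0.56 times the within-visit SD. A reader might take 2.3 to 4.5 mmHg as the bias of the plan. The documents do not support that: it needs the worst value to take precedence over the later one, worst to be one-sided, and an assumed SD of 4 to 8 mmHg. The zero at the other end needs a two-sided worst and patients centred on the reference.

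Nor does this weaken the safety evaluation as a whole. The primary endpoint (TEAEs), the other AE analyses, the listings, and the last, minimum and maximum values are unaffected. No hypothesis is tested.

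**What to change.** In SAP 6.7 and 7.8.3:

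- Use the pre-dose reading for by-visit values and for change from baseline.
- Summarise post-dose readings as a separate planned time point, with a stated slot for Day 1.
- Limit the same-day rule to true repeats at the same planned time point. State whether it takes precedence over the later-value rule, and define the direction of worst for each vital sign.
- If a sponsor standard already does this, cite it in 7.8.3 instead.

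A table of post-dose minus pre-dose change is optional. The cost is SAP wording, a little more programming and one extra table. Both readings are already collected, so nothing changes at the sites.
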